- 21.1 * Click on the gray bar below and provide a synopsis of the research study/project addressing the following SIX items USING these numbered subheadings:
 - 1. Purpose,
 - 2. Rationale,

- 3. Study/Project Population,
- 4. Research Design,
- 5. Study/Project Procedures, and
- 6. Outcome Measures.

Title: Memphis Superheroes Club

1. Purpose,

The primary purpose of this project is to develop and implement the culturally-tailored, comprehensive, and out-of-school program, Insulin Superheroes Club (ISC). This is a diabetes prevention program for youth based on the CDC curriculum designed for adults. This will be accomplished through collaborations with the University of Tennessee Health Science Center (UTHSC), Le Bonheur Children's Hospital (LBCH), and the YMCA. The goals are to improve participant health and prevent diabetes by improving metabolic parameters, physical fitness, and health habits.

2. Rationale, Background and Significance:

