Along with decrease beta-cell function, youth with type 2 diabetes become resistance to pharmacological mono-therapy (metformin or rosiglitazone) and lifestyle intervention such as change in diet and physical activity. Due to these limiting factors, once a pre-diabetic child or adolescent develops type 2 diabetes, it is considered irreversible (Zeitler et al, 2012.) Given this, the focus is on early prevention of on-set prediabetes or type 2 diabetes among the obese youth population. Early lifestyle prevention and intervention programs consist of changing diet, physical activity and lifestyle habits (i.e taking the stairs instead of the elevator) through education. A number research study-programs have shown promising results in regards to diabetes prevention such as: 42% reduction of whole body insulin sensitivity, a two- fold greater change in body fat than body weight, increase lean body mass, and normalized fasting, two-hour plasma blood glucose levels, and decrease LDL cholesterol levels (Shaw, 2009, Wadden, 2012.) In addition to the physical and metabolic impact of obesity, research supports the relationship between obesity, mental health, and health behaviors. Generally, overweight and obese youth have increased mental health concerns compared to their normal weight peers (Sinha, 2002.) Specifically, obesity has been linked to presence of depression, anxiety, attention deficit hyperactivity disorder, and conduct disorder among children (Halfon, 2013, Puder, 2010.) Difficulty coping with stress and decreased selfesteem are also associated with obesity (BeLue, 2009.) Studies have also shown that individuals, adults and youth, with type 2 diabetes have decreased cognitive functioning including mental processing speed, flexibility, memory, and learning (Puder, 2010.) Physical activity participation has been linked with improved academic performance, mental health, and cognitive function (Hillman, 2008.) Despite these findings, the best treatment or weight management for childhood obesity is still uncertain. A few studies have examined the cumulative impact of improving physical activity, fitness, nutrition, and overall health behaviors in children.

The specific aims of this research project are to:

- 1) Examine the change of health status of youth participants over time as a result of the 12-month (16 weekly, 3 biweekly, and 6-monthly session) ISC intervention through the evaluation of metabolic, physical fitness, and health habit parameters

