- 2) Examine the change of health status of parent participants over time as a result of the 12-month (16 weekly, 3 biweekly, and 6-monthly session) DPP adult sessions through the evaluation of metabolic, physical fitness, and health habit parameters.

3. Study/Project Population,

Potential subjects and their parents will be informed of the study through flyers, community events, and physician referrals. Flyers will be distributed/posted at all YMCA sites and physician offices and clinics, throughout Memphis.

Inclusion criteria for youth participants will include:

- 1) Between 7-15 years-old
- 2) Hemoglobin A1C 5.7-6.4% or BMI \geq 85th percentile, parent **or** grandparent with pre/type II Diabetes
- 3) Able to participate in physical activity
- 4) Parent or caregiver participation

Exclusion criteria for youth participants will include:

- 1) Pregnant females
- 2) Those with mental health illness (e.g. depression, ADHD, etc.)
- 3) Medications that would interfere with testing results (e.g. metformin, insulin)

Inclusion criteria for parent participants will include:

- 1) ≥18 years-old
- 2) At least one child enrolled in ISC
- 3) Able to participate in physical activity

Exclusion criteria for parent participants will include:

- 1) Those with mental health illness (e.g. depression, ADHD, etc.)
- 2) Medications that would interfere with testing results (e.g. metformin, insulin).

Inclusion and exclusion criteria will be assessed via parent and child self/physician referral form. The UTHSC/LBCH subcommittee will approve all procedures for the Use and Protection of Human Subjects. ISC and control group participants will be assigned on a fist come first serve basis.

Consenting and Questionnaires:

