On the day of registration, parents or guardians will receive project information packets from the trained research team. The packets will include a parent/guardian consent form, a child assent form, and detailed participation requirements, benefits, and incentives. Once the researcher consents the parent and assents the child face-to-face, the child and parent will be asked to sit with the researcher to complete the study questionnaires. The parent will complete the Healthy Habits Questionnaire (parent version), the child and parent will complete the Healthy Habits Questionnaire (child version), and the child (child version) and parent (parent version) will complete the mental health questionnaire separately. Trained research team members will complete all face-to-face consenting and surveys/questionnaires. Upon consenting the family (parent and child/children) will be assigned, to either the ISC. Once completed the participant will return the following week to complete their pre-evaluation assessment.

The parents will be encouraged to contact the research team if they should have any questions regarding the study procedures. All questionnaires, consents, and assent forms must be completed prior to the data collection days with the assistance of a research team member. The research staff will review all materials and assign a study id prior to the child's participation in data collection. Following completion of the project parents or guardians of all children enrolled in the project will receive a report of their health behaviors, physical fitness, and mental health performance with strategies to improve/maintain their outcomes. The research team member will also inform the parent and child that video recording and pictures of the educational sessions, physical activity sessions, and evaluation sessions (only physical fitness measures) will be taken by a research team member for the use of dissemination and presentations regarding the findings. If parents do not wish to consent and child does not wish to assent to video recordings or photography of this nature the research team will make a note and respect the participants' wishes.

4. Research Design,

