Persons	Who Are Institutionalized as Mentally III	
☐ Students	s of a School Associated with this Project	
☐ Employe	ees of an Institution/Agency Associated with this Project	
Dl1-:		
Please explai	in how a certain category of vulnerable subjects might be incidentally included:	
26.0 (14	194) Study/Project Duration	
26.1 * Wha	at is the anticipated duration of a single subject's participation in the study/project?	
	ar is the material and money a surged of participation in the setting, projects	
1 year		
26.2 * How	v long will the entire study last locally, including time for data analysis?	
5 years		
27.0 (15	500) Inclusion Exclusion Criteria	
27.1 Identi	fy inclusion criteria.	
Order		
Number	Criteria	
1	1) Ages 7-15	
	Parent Inclusion Criteria: 18 and older	

1	
2	2) Prediabetes-A1C 5.7-6.4% ${f or}$ BMI of an 85th percentile or above ${f or}$ a grandparent /parent with diabetes
2	Parent Inclusion Criteria: at least one child enrolled in ISC
3	3) Able to participate in physical activity
3	Parent Inclusion Criteria: Able to do physical activity
4	4) Parent enrolls in the adult DPP

27.2 Identify exclusion criteria.

Order Number	Criteria
1	1) pregnant females
1	Parent Exclusion Criteria: those with mental disorder (e.g. depression, ADHD, etc.) and/or severe mental illness which requires immediate treatment (e.g., active psychotic episode)
2	2) those with mental disorder (e.g. depression, ADHD, etc.) and/or severe mental illness which requires immediate treatment (e.g., active psychotic episode)
3	3) medications that would interfere with testing results (eg. metformin, insulin)
3	Parent Exclusion Criteria: medications that would interfere with testing results (eg. metformin, insulin)

28.0 (1600) Subject Selection and Recruitment					
28.1 * How will subjects be selected?					
* Subjects identified through medical record screening					
⊙ Yes ○ No					
* Contact by investigator with his/her patients in the clinical setting					
⊙ Yes ○ No					
* Referral from non-investigator practitioner					
⊙ Yes C No					
* Subjects recruited from among students and/or employees					
O Yes ⊙ No					
* Telephone pre-screening					

* Website pre-screening	
C Yes No	
* Advertising	
* Other	
O Yes O No	
28.2 * Recruitment Materials	
At the end of this application, you are required to attach all recruitment materials which you intend to use for this study /project.	

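### The 6.4% A1C ceiling covers only the prediabetes entry route and 27.2 does not exclude diabetes, so a child who already has untreated diabetes can enter a prevention programme

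*Combined protocol and SAP*

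**What the plan says.** **Entry.** Section 27.1 item 2 gives children three alternatives joined by *or*: "Prediabetes-A1C 5.7-6.4"%, "BMI of an 85th percentile or above", or a grandparent or parent with diabetes. The synopsis (21.1 item 3) words the same criterion differently. It begins "Hemoglobin A1C 5.7-6.4% or BMI" and then has a comma, where 27.1 has its second *or*, before the family-history element.

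**Exclusion.** For children, 27.2 lists pregnancy, mental disorder, and "medications that would interfere with testing results (eg. metformin, insulin"). Neither 27.2 nor 21.1 item 3 names diabetes or an A1C ceiling.

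**Screening and timing.** Under 29.1, research staff or the referring professional apply the listed criteria. Section 21.1 item 3 says they are assessed through a self or physician referral form. The first A1C taken by the study is at the pre-evaluation (Visit 2), after consent and registration at Visit 1 and before Session 1 at Visit 3.

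**Afterwards.** Discontinuation and withdrawal criteria (34.1) are answered as not applicable. Section 31.1 offers follow-up routes for abnormal incidental findings.

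**Purpose.** Section 21.1 item 1 states: "This is a diabetes prevention program for youth based on the CDC curriculum designed for adults". The rationale (21.1 item 2) says that "youth with type 2 diabetes become resistance to pharmacological mono-therapy (metformin or rosiglitazone) and lifestyle intervention such as change in diet and physical activity", and that "once a pre-diabetic child or adolescent develops type 2 diabetes, it is considered irreversible".

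**The concern.** The upper limit on the first route shows that the authors meant the prediabetes group to stop at 6.4%. Because the routes are alternatives, that limit binds no child who qualifies in another way. The only nearby exclusion concerns drugs, and its stated reason is interference with test results. It removes children treated with metformin or insulin. It leaves those whose diabetes is undiagnosed, untreated or managed by diet.

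Two things are at stake. The first is fit of sample to purpose: on the plan's own rationale, such a child already has the condition to be prevented and belongs to a group described as resistant to lifestyle intervention. The second is the child's welfare: the study would hold an A1C above its own prediabetes band, and no sentence says that a scheduled A1C result, as distinct from an incidental finding, goes down the 31.1 route.

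**Working it through.** The plan gives no figure to reproduce. The question is one of eligibility logic, so the check is an enumeration.

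**Inputs**
- *A*: A1C between 5.7 and 6.4% (27.1 item 2; 21.1 item 3)
- *B*: BMI at or above the 85th percentile (same places)
- *F*: qualifying family history (same places)
- *M*: taking an interfering drug such as metformin or insulin (27.2)
- Test case: A1C 6.5%, the first one-decimal value above the plan's ceiling, so *A* is false. All other criteria are taken as met.

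**Rules**
1. Section 27.1: (*A* or *B* or *F*) and not *M*. With *A* false this becomes (*B* or *F*) and not *M*.
2. Synopsis with the comma read as *and* over both earlier elements: (*A* or *B*) and *F* and not *M*. This becomes *B* and *F* and not *M*.
3. Synopsis with family history attached to BMI only: (*A* or (*B* and *F*)) and not *M*. This also becomes *B* and *F* and not *M*.

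If the comma is read as *or*, the synopsis is the same as rule 1.

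**Result for a child at 6.5%** (four combinations of *B* and *F*)

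| Rule | No interfering drug | On metformin or insulin | With A1C below 6.5% also required |
|---|---|---|---|
| 1 | 3 of 4 eligible | 0 of 4 | 0 of 4 |
| 2 | 1 of 4 | 0 of 4 | 0 of 4 |
| 3 | 1 of 4 | 0 of 4 | 0 of 4 |

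Under rule 1 the eligible profiles are high BMI alone, family history alone, and both. Under rules 2 and 3 the one eligible profile is high BMI together with family history. The gap narrows under the stricter readings but does not close. The drug exclusion closes it only for treated children. The last column shows that the missing ceiling is the cause; it is not the proposed rule, because excluding on one fingerstick reading would be too blunt.

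These counts are of logical profiles, not children. Section 24.1 plans 100 subjects, children and adults together, and does not say how many are children. Nothing in the documents gives a rate of A1C above 6.4%. No expected number can be computed.

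**The case against.** The strongest reply is that the consequence for the analysis is small or absent.

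- **No endpoint is incident diabetes.** Aim 1 concerns change in metabolic, fitness and health-habit measures, and the goals include improving health generally. The sample is mixed by design. A reader might infer that enrolling a child with diabetes invalidates or biases Aim 1, but the documents do not support that. One high value widens the spread between children at baseline. The analysis, however, is of repeated measures over time, and a constant offset in one child cancels in that child's own change. This stands.
- **Three separate routes are not certain.** If family history is conjunctive in 21.1, it is not a route of its own. This also stands, and it narrows the gap without closing it.
- **Screening may catch known cases.** The referral form is not available and could ask about diagnosed diabetes. Medical-record screening (28.1) or an A1C from a referring doctor (PHI description before 56.2) could also reveal it. A reader might infer that screening cannot detect these children; that goes too far. What can be said is that no written criterion acts on what is found.
- **Follow-up exists.** Section 31.1 offers referral or study-doctor follow-up, and a medical director supervises the metabolic measures (21.1 item 5). The selected option is not legible in the available text, which is no fault of the plan. It would be wrong to infer that a high value goes unattended. The plan only fails to say that a scheduled A1C counts.
- **Assignment at consent is weak evidence.** The sentence "Upon consenting the family (parent and child/children) will be assigned, to either the ISC" looks like a remnant of a two-group design, and Visit 2 precedes Session 1 in any case. The point does not rely on it.

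**Conclusion.** The gap is certain on the text. A child above 6.4% who takes no interfering drug is eligible through BMI (together with family history on the stricter readings of 21.1) and, under 27.1, through family history alone. This contradicts the stated prevention purpose and the plan's own rationale.

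Its size is unknown. The number of such children may be zero, and no distortion of Aim 1 has been quantified. The conclusion rests on the written criteria; a diabetes question on the referral form would reduce the practical exposure to children not yet diagnosed. Severity is minor to moderate: worth correcting because the correction is cheap and serves both the coherence of the sample and the safety of the child, not because the analysis is shown to fail.

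**What to change.** 1. **Sections 27.2 and 21.1 item 3, youth exclusions.** Add: *known diabetes, or diabetes confirmed after a Visit 2 A1C of 6.5% or above*. Use the same punctuation for the entry criterion in 27.1 and 21.1.
2. **Section 31.1.** Add: *A child's scheduled A1C of 6.5% or above is reviewed by the medical director and referred by the route selected here. The Visit 2 value is reviewed before Session 1.*
3. **Analysis text (21.1 item 6 and 34.3).** A child with a high Visit 2 value stays in the analysis unless diabetes at entry is confirmed by a fixed date, for example before the Week 8 evaluation. Report Aim 1 A1C results with and without any child at 6.5% or above at Visit 2. A child who first crosses 6.5% later stays in, with all values kept.
4. **Data capture.** Record the start date of any glucose-lowering drug, since 27.2 governs such drugs only at entry and an A1C fall after starting one could be mistaken for a programme effect in a single-group design.

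Requiring confirmation avoids removing a child on one fingerstick, and the fixed date stops membership of the analysis set from drifting. The rule is limited to children, because parents have no A1C criterion.

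**Cost.** One exclusion line in two places, a few sentences in 31.1 and the analysis text, one REDCap date field, one extra tabulation, and possibly a matching line in the consent and assent forms. No study visit is added, as Visit 2 already includes the A1C. The downsides are that a few children may leave the analysis sample, and that confirmation depends on a clinical test outside the study, which some families may not obtain by the cut-off. Reporting both ways shows how much that matters.

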Engagement in regular physical activity is widely accepted as an effective preventative measure for a variety of health risk factors across all ages, genders, race/ethnicities, and socioeconomic groups (Janssen, 2010.) However, levels of physical activity remain low and obesity rates continue to rise (Odgen, 2014,) with significant disparities among Hispanic and African-American youth, nationally and specifically in Tennessee (Tennessee Department of Education, 2008.) The impact of obesity is evident in the worsening rates of metabolic functioning, especially among children who are experiencing greater rise in blood pressure (National Center for Chronic Disease Prevention and Health Promotion (NIHCM), 2008,) hyperlipidemia (NIHCM, 2008,) and increased prevalence of type 2 diabetes (Sinha, 2002.) Type 2 diabetes occurs when there is an imbalance between insulin secretion and insulin resistance. Among youth populations, the prevalence of developing type 2 diabetes increases during puberty due to the natural transient state of insulin resistance (Caprio, 1989.) Type 2 diabetes in youth when compared that in adults has particular characteristics; the transition from glucose deregulation to overt diabetes occurs at a faster rate. In adults, the transition from pre-diabetic to a diabetic state takes about 10 years with a 7% reduction of beta cell function per year (Kahn, 2001, Matthews, 1998.) In pre-diabetic youth, the mean transition period is significantly reduced to about 2.5 years with a 15% reduction of beta cell function per year (Gungor, 2004.)

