Health Behaviors. A Healthy Habits Questionnaire (HHQ) will be used to measure knowledge and behaviors toward developing a healthier lifestyle. The Healthy Habits questionnaire will take approximately 30 minutes to complete and will be administered by a research team member. These questions will be completed by the child and parent and includes questions about: demographics (i.e. age, race/ethnicity, SES, home environment); child's academic status; family health history; weight perception, and frequency and range of typically consumed foods, exercise, sleep, and healthy-living behaviors. To obtain a valid measure, questions from previously published school-based intervention studies will be selected (Prochaska, 1994; Perry, 1998; Stevens, 1999) and reviewed by our team of experts. The parent-child relationship will be assessed with measures of parent involvement (BeLue 2009) parent monitoring (O'Donnell, 2002) and family cohesion (Resnick, 1997.)

Evaluation Measures:

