 No recruitment materials will be used in this research. Recruitment materials to be used in this research will be attached at the end of this application. Recruitment materials will be submitted at a later date. 	
* Describe how/where EACH of your recruitment materials (by name) will be used, in the text box below; e.g., on a website, sent to an email list, posted on campus, in a newspaper, etc.	
Flyers and project information that will be posted on campus and throughout the community.	
29.0 (1710) Study/Project Procedures	
29.1 * Describe the procedures that will be performed to determine whether prospective subjects satisfy inclusion /exclusion criteria for study/project participation.	
* Medical Record Review should be included as a procedure if it is used to determine whether prospective subjects satisfy the criteria for study/project participation.	
Prospective subjects will be screened by a research staff personnel or screened by a health professional that is referring the participant. They will determine whether they qualify for the program if they meet the inclusion/exclusion criteria.	
29.2 * Do the study/project procedures involve administration of a drug, device or other intervention to determine its efficacy, safety, and/or tolerability for treatment purposes?	
 Yes. The study/project procedures involve administration of a drug, device or other intervention to determine its efficacy, safety, and/or tolerability for treatment purposes. No. The study/project procedures DO NOT involve administration of a drug, device or other intervention to determine its efficacy, safety, and/or tolerability for treatment purposes. 	
30.0 (1730) Procedures other than Treatments	

30.1 * Describe all procedures, other than treatments, that will be performed.

For studies/projects that involve multiple study/project visits, specify the timing of each visit, and in chronological order, list what will be done at each visit.

Click on "Add a new row" to list each procedure of each visit.

If you do not wish to use the table, click on the Text Editor and type in the information (specify the timing of each visit and list in chronological order, using bullet points, what will be done at each visit).

Also use the Text Editor to further describe any procedures that are not self-explanatory.

Visit Name	Visit Timing	Procedure
Consent, registration	1-2 hours	Consenting
Pre-evaluation	1-2 hours	Pre-evaluation see below for details

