Mid-evaluation	1-2 hours	Mid-evaluationsee below for details
post-evaluation (3 month)	1-2 hours	post-evaluationsee below for details

Consent, register participants, questionnaire completion

• The first visit will be for program registration and consenting at the Gaisman Community Center. Research staff will consent parents, assent children, and sit face-to-face with the parent and child to complete the Healthy Habits and mental health questionnaire. This will take about 1-2 hours to complete.

Pre-Evaluation

• All physical activity, physical fitness, and health measures described will be collected at the Gaisman Community Center. This will take about 1-2 hours to complete. The drop-off/pick-up home visit appointments will also be scheduled in order to collect physical activity data described in the health behaviors measures. The child will be asked to wear the activity monitor for 7-days hours. The drop-off home will take 30 minutes. The pick-up home visit will take 30 minutes. Both home visits will add up to 60 minutes to complete.

Mid-Evaluation

• All physical activity, physical fitness, and health measures (except the blood glucose and cholesterol) described above will be collected at the Gaisman Community Center. This will take about 2 hours to complete.

Post-Evaluation

• Research staff will sit face-to-face with the parent and child to complete the Healthy Habits and mental health questionnaire. All physical activity, physical fitness, and health measures described above will be collected. This will take about 1-2 hours to complete at the Gaisman Community Center. The drop-off/pick-up home visit appointments will also be scheduled in order to collect physical activity data described in the health behaviors measures. The child will be asked to wear the activity monitor for 7-days. The drop-off home will take 30 minutes. The pick-up home visit will take 30 minutes. Both home visits will add up to 60 minutes to complete.

31.0 (1731) Incidental Findings

31.1 * How will abnormal incidental findings be handled?

- The subject will be referred for follow-up to his/her primary care physician.
- The study doctor will provide follow up for the abnormal finding.
- Other
- O Not Applicable; incidental findings are not expected in this project.

32.	0 (1733) Creation of Specimen & Data Repositories/Registries	

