32.:	* Does this study include creating a specimen repository or a data registry/repository? A repository is established when there is a plan to make stored data and/or specimens available for later use in other research studies.	being
	Yes No	
33.	0 (1734) Use of Other Data/Specimen Repositories	
33.:	1 * Will this project/study involve using data/specimens from other repositories?	
	Yes No	
34.	0 (1735) Discontinuation, Endpoints, Analyses	
34.:	1 * Describe the criteria for discontinuation of treatment and withdrawal of the subject from the study/project.	
N/A	A	
34.2	2 * Describe the endpoints or outcomes being assessed in the study/project, such as efficacy and safety endpoints.	
Ch Ba: Ch Ba: (Ti	tcome Measures: ange Over Time: Intervention seline (Time: 0) by changes over time (mid-intervention (Time: 1), and post-intervention (Time: 2)) ange Over Time: Maintenance seline (Time: 0) by changes over time (3-months out (Time: 3), 6 months out (Time: 4), 9 months out me: 5), 12 months out (Time: 6) st-intervention (Time: 2) by changes over time (3-months out (Time: 3), 6 months out (Time: 4), 9 onths out (Time: 5), 12 months out (Time: 6))	
34 1	3 * Describe the statistical analysis that will be used.	
J-7	Describe the statistical analysis that will be used.	
Phyto how physical ph	mary Predictors: ysical Activity: An accelerometer (Computer Science and Applications, Inc., Shalimar, FL), will be used assess physical activity. To ensure good reliability of devices used, children and parents will be taught w to use the accelerometers and reminded to wear them via a phone call. Self-report measures of ysical activity and sedentary habits will also be obtained. ysical fitness (cardiorespiratory, muscular strength and endurance, and motor skills): The fitness ttery will include the American Thoracic Society six-minute Walk Endurance Test (aerobic fitness) while onitoring pulse oximeter (blood oxygen), Jamar plus handgrip dynamometer (grip strength), MicroFET-2 indheld dynamometer (maximal isometric strength), sit-and-reach box (lower body flexibility), 30-foot uttle run (agility), and Bruininks-Oseretsky Test of Motor Proficiency (fine and gross motor control	

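### Drugs the plan regards as interfering with the tests are excluded only at entry; no described procedure records drug starts in the following year, so their effect would be counted as programme change

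*Combined protocol and SAP*

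**What the plan says.** The synopsis (21.1, item 3) excludes "Medications that would interfere with testing results (e.g. metformin, insulin") for children and, in a separate list, for parents. Section 27.2 repeats this for both: "medications that would interfere with testing results (eg. metformin, insulin").

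The check belongs to screening. Under 29.1, research staff or the referring professional assess prospective subjects: "They will determine whether they qualify for the program if they meet the inclusion/exclusion criteria". The synopsis says the criteria are assessed from a referral form.

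After entry:

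- Participation lasts one year (26.1), with evaluations at Visits 2, 11, 20, 25, 29 and 33 (21.1, item 5). A1C, lipids, blood pressure and body composition are outcomes. Blood glucose and cholesterol are omitted at Visit 11.
- The visit descriptions in 21.1 and 30.1 list no medication check. The Healthy Habits Questionnaire topics are demographics, academic status, family health history, and "weight perception, and frequency and range of typically consumed foods, exercise, sleep, and healthy-living behaviors".
- Section 34.1, "Describe the criteria for discontinuation of treatment and withdrawal of the subject from the study/project", is answered N/A.
- The covariates are race, ethnicity, SES and age, plus BMI-Z in the synopsis or grade in 34.3. Neither list includes medication, and neither paragraph mentions values obtained after a drug start.

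The design paragraph (21.1, item 4) describes an intervention group without a control. The aims attribute change over 12 months to the programme, for children (Aim 1) and for parents (Aim 2).

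**The concern.** By its own exclusion rule, the plan accepts that certain drugs distort its measurements. That holds equally for a participant who starts such a drug in month five, but the plan has no means of seeing it. The later values would enter the change-from-baseline analysis alongside all others. With one group and no medication record, the drug's contribution can be neither separated from the programme's nor corrected afterwards.

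For a glucose-lowering drug and A1C, the shift would usually favour the programme: a participant who worsens and is then treated shows a lower value than the programme alone would have produced. For weight, lipids and blood pressure the direction depends on the drug. What is at stake is whether a reported change over the year can be read as the programme's effect.

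**Working it through.** **Document figures.** The plan gives no alpha, power, SD, drug-start rate or sample-size derivation, so there is no figure to reproduce. Section 24.1 gives an accrual of 100, covering children and parents together and including screen failures and withdrawals. An analysis of children or parents alone would be smaller.

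**Where a drug start could be seen.** The questionnaires are scheduled at Visits 1, 20 and 33. Visits 11, 25 and 29 list only activity, fitness and health measures. Even if a questionnaire held a medication item, none would be asked at the mid, 6-month or 9-month evaluation.

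**When it affects the outcomes.** A1C and lipids are not taken at Visit 11, so for these a drug start matters from Visit 20 onward. Blood pressure and body composition can be affected from Visit 11.

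**Illustration of size (all inputs assumed).** Let f be the fraction starting a drug, d the drug's effect in SDs of change, and n the number analysed. Assume no programme effect, a one-sample two-sided test at 0.05, and a drug acting in the favourable direction.

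- Bias in mean change: b = f × d
- SD of change: s = √(1 + f(1 − f)d²)
- Shift of the test statistic: δ = b√n / s
- Rejection rate: Φ(δ − 1.96) + Φ(−δ − 1.96)

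For f = 0.10, d = 1, n = 100: b = 0.10; s = √1.09 = 1.044; δ = 0.10 × 10 / 1.044 = 0.958; the rate is 0.158 + 0.002 = 0.160.

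| Fraction starting | Bias (SD), d = 1 | False-positive rate, n = 100 | n = 50 |
|---|---|---|---|
| 2% | 0.02 | 5.5% | 5.2% |
| 5% | 0.05 | 7.8% | 6.4% |
| 10% | 0.10 | 16.0% | 10.4% |
| 20% | 0.20 | 45.9% | 25.9% |

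With n = 100 and d from 0.5 to 1.5, the rate runs from 5.1% to 6.0% at 2% starting and from 7.8% to 27.7% at 10%.

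**On the A1C scale.** With an assumed drug effect of 0.1 to 0.5 point, the mean shifts by 0.02 × 0.1 = 0.002 point at the low end (2% starting) and by 0.20 × 0.5 = 0.10 point at the high end (20% starting). At 10% starting it is 0.01 to 0.05 point.

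**The case against.** The strongest reply is that the gap may be small or already covered. The questionnaires, the referral form and the database dictionary are not in the documents, and a medication item may exist. This stands as a limit: the finding is that no described procedure or listed topic covers medication, not that none exists. An existing item would answer part of the recording question but would not supply the missing analysis rule.

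The size also depends wholly on an unknown drug-start rate, and at about 2% the problem is negligible. That stands too. Without a record, however, the sponsor could not show which case applied.

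Several stronger readings are tempting but not supported:

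- **That drug starts are likely.** A reader might infer this from "The subject will be referred for follow-up to his/her primary care physician" in 31.1, from "Contact by investigator with his/her patients in the clinical setting" in 28.1 (answered Yes), or from the obesity programme named in 36.1. In 31.1 the selected option cannot be read. Section 28.1 concerns recruitment. Section 36.1 names the programme for data and statistical support and says nothing of prescribing.
- **That a drug-start rate follows from the rationale's statement** "In pre-diabetic youth, the mean transition period is significantly reduced to about 2.5 years". This concerns pre-diabetic youth. Under 27.1, children may also enter on BMI or family history alone; parents have no A1C criterion, and the same paragraph gives about 10 years for adults. Transition to diabetes is also not the same event as starting a drug.
- **That every outcome is biased towards the programme.** Only metformin and insulin are named. Other drugs fall under the rule's general wording, but their direction is not given.
- **That 34.1 contradicts the exclusion.** Eligibility and withdrawal are separate matters. The N/A means only that no rule for later drug starts is found there.

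Finally, Aim 3 in 22.1 and a sentence in 21.1, item 3, still mention a control group, at odds with the design paragraph. Even with one, unrecorded starts could differ between groups.

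**Conclusion.** The point holds as a gap in data capture and analysis. As written, the plan would mix values that its own exclusion rule treats as unreliable into the estimate of change, with no described record from which to detect or correct this. The size cannot be fixed from the documents. Under the stated assumptions it is negligible at about 2% starting a drug and material at about 10% or more (n = 100, effect of 1 SD: about 16% false positives against a nominal 5%). For A1C the distortion would usually favour the programme; for weight, lipids and blood pressure the direction is open. The conclusion rests on the single-group design in 21.1, item 4, and on the questionnaires containing no more than the documents describe. It should be corrected because the remedy is cheap and start dates not collected at the time may not be recoverable.

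**What to change.** 1. At Visits 2, 11, 20, 25, 29 and 33, record for each child and each participating parent the current use and start date of any drug that could affect the measured outcomes.
2. In 34.3, keep the analysis of all data and prespecify a sensitivity analysis that excludes values obtained after a drug start. Use a likelihood-based mixed model that keeps each participant's earlier values. A repeated-measures ANOVA that drops incomplete participants would remove those who started a drug, and if these are the ones who were worsening, the result would again favour the programme. State the missing-at-random assumption and acknowledge that it may fail for the same reason.
3. Report the number who started such a drug beside the results, and qualify any claim of programme benefit if the two analyses differ.

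The cost is a short form at visits already scheduled, one additional analysis, and a somewhat less precise sensitivity estimate. The change concerns recording and analysis only; it bears on no treatment or withdrawal decision.
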